### 8.2 Sample Size Determination

Approximately 1000 participants will be randomly assigned to study intervention for an estimated total of 500 participants per intervention group with one-sided alpha of 2.5% and an approximate power of 90%. Since the OPC test does not require a statistical significance level, this study is powered for the NI test.

The assumed primary outcome rate is 1.75%/pt-yr with warfarin based on a review of literature available with the On-X aortic devices (Puskas et al., 2018; Tossios et al., 2007; On-X Original PMA #P000037, 2001; McNicholas et al., 2006; Chambers et al., 2013; and Wu et al., 2006). It was assumed that all historical trials enrolled a mixture of high and low risk population (HRP and LRP), but only the PROACT clinical trial (Puskas et al., 2014; Puskas et al., 2018) reported the proportion of high and low risk populations (65% and 35% respectively), which was taken into account to estimate the primary outcome rate for the trial.

The thromboembolism (TE), thrombosis and valve-related mortality (VRM) rates are coincident to the remaining events in the composite. Thus, the sample size will be based on a composite of TE, thrombosis and VRM rates. Except for the PROACT clinical trial data, the publications report the non-hierarchical event rate for VRM and TE. If a participant died due to a TE, it would be counted in both the VRM and the TE rate. The trial by Tossios et al., 2007 report the number of deaths related to TE (n=5) and all valve-related deaths (n=19). The percent of deaths due TE is 26%. It was assumed that for any publication that did not report the number of deaths related to TE that 26% of the deaths were due to TE. Thus, the VRM rates are reduced by 26%.

**Table 3** (see section 11) summarizes the available literature, the event rates and their variances. Since the number of historical trials to estimate the event rate in warfarin arm is not large, the Hartung-Knapp-Sidik-Jonkman (HKSJ) method was used to produce more robust estimates of variance of the event rate (IntHout et al., 2014). The pooled event rate of warfarin was estimated as 1.75%/pt-yr with a 95% confidence interval of 1.09%/pt-yr and 2.81%/pt-yr by a random effects HKSJ meta-analysis model with the R metafor package. We project that there will be a similar event rate with apixaban and set the non-inferiority margin for this study at 1.75%/pt-yr, equivalent to a doubling of the estimated event rate in warfarin arm.

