To confirm that the non-inferiority margin preserves the treatment effect, we would need to estimate the treatment effect for the use of warfarin post-implantation as compared to placebo. There are no placebo-controlled trials of warfarin for patients with AVR. In the PROACT trial that randomized low risk AVR patients to warfarin (INR 2.0-3.0) or dual antiplatelet therapy (DAPT), the warfarin arm had a hazard rate of 1.15%/pt-yr and the DAPT arm had a hazard rate of 7.02%/pt-yr (detailed in Section 11, **Table 4**). Given the substantially higher event rate in the DAPT versus warfarin arm, we have conservatively assumed that DAPT was a placebo equivalent. Though not ideal, the treatment effect calculated from this data will be conservative (i.e., smaller) than the treatment effect estimated from a true placebo arm. However, the trial involving DAPT enrolled only low risk AVR patients (i.e., no chronic atrial fibrillation, left ventricular ejection fraction > 30 %, left atrium < 50mm diameter, no spontaneous echo contrasts in the left atrium, no neurological events, no hypercoagulability, and no left or right ventricular aneurysm).

To extrapolate these results to an all-comer AVR population, we employed a conversion factor. The event rate for warfarin in the low risk population is 1.15%/pt-yr, the meta-analysis above demonstrated a pooled event rate of 1.75%/pt-yr for warfarin-treated patients (INR 2.0-3.0), therefore the conversion factor was calculated to be 1.52 (= 1.75/1.15). The number of observed events (95% CI) with 26% reduction to VRM for TE overlap of DAPT in the low risk population is 20.2 (13.00, 30.89) using the Poisson distribution, which translated to an event rate (95% CI) of DAPT arm of 7.02% (4.51%/pt-yr, 10.72%/pt-yr). Multiplying by the conversion factor of 1.52, the DAPT event rate (95% CI) in an all-comer AVR population is 10.65%/pt-yr (6.85%/pt-yr, 16.28%/pt-yr).

Table 2 presents the estimated event rates and confidence intervals for warfarin, DAPT and apixaban in all-comer AVR population. Even if an event rate in apixaban arm is 5%/pt-yr, which is unlikely, the estimated upper 95% CI of the apixaban arm will still remain below the lower 95% CI of the event rate of DAPT.

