**Table 2. Event rates and confidence intervals for warfarin, DAPT, and apixaban in all-comer AVR population.**

Treatment in all-comer AVR population	Event rate (%/pt-yr)	Lower 95% CI (%/pt-yr)	Upper 95% CI (%/pt-yr)
Warfarin*	1.75%	1.09%	2.81%
DAPT†	10.65%	6.85%	16.28%
Apixaban†	1.00%	0.52%	1.66%
	1.25%	0.71%	1.98%
	1.50%	0.90%	2.30%
	1.75%	1.10%	2.60%
	2.00%	1.30%	2.91%
	2.25%	1.50%	3.21%
	2.50%	1.71%	3.51%
	3.00%	2.13%	4.10%
	4.00%	2.98%	5.27%
	5.00%	3.86%	6.42%

\* The confidence interval was estimated using the random effects HKSJ meta-analysis model; † The confidence intervals were estimated using Poisson distribution.

Assuming that the event rates for warfarin and apixaban would be similar, a conservative estimate of the treatment effect is 4.04%/pt-yr, which reflects the difference between the upper bound of the 95% CI of the pooled event rate of warfarin (2.81%/pt-yr) and the lower bound of the 95% CI of the event rate in DAPT (6.85%/pt-yr). The non-inferiority margin of 1.75%/pt-yr is approximately 43% (1.75/4.04) of the treatment effect and below ½ of the treatment effect as cited in the 2016 FDA guidance “Non-Inferiority Clinical Trials to Establish Effectiveness Guidance for Industry” ([CDER/FDA, 2016](#)).

With an accrual time of 1 year, an assumption that 50% of the expected number of participants will be enrolled in about 5 months (40% of the total accrual time), and a minimum follow-up period of 2 years, the assumed loss to follow-up rate for the period of 2 years is 5%, which is equivalent to a loss hazard rate of 0.026 for both the test and control groups. *Assuming a one-sided alpha of 2.5%, an approximate power of 90%, an equal event rate of 1.75%/pt-yr in both warfarin and apixaban arms, and an absolute NI margin of 1.75%/pt-yr, the estimated sample size is 990, therefore this study will recruit approximately 1000 participants.*

The major bleeding hazard rate for the control group is assumed to equal 3.63%/pt-yr ([Puskas et al., 2018](#)). The reference value was calculated by summing up numbers of events and follow-up years from both high and low risk controls. Using the proposed sample size of 1000, a superiority test for major bleeding has 90% power to detect a difference of 2.13%/pt-yr (i.e., 3.63%/pt-yr for warfarin arm and 1.5%/pt-yr for apixaban arm).

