## 11 References for sample size calculation

**Table 3. References used to estimate the primary outcome rate of warfarin (%/pt-yr).**

Author	Chambers	McNicholas	On-X Original PMA# P000037	PROACT		Tossios	Wu
				High Risk Control	Low Risk Control		
Year	2013	2006	2001	2018		2007	2006
Country	UK, Spain, Greece	USA	Germany, Spain, Greece	US, Canada		Germany	South Africa
Sample size	214	142	184	190	102	264	104
% of total	18%	12%	15%	16%	9%	22%	9%
Mean patient age (yrs)	59.7	58.6	60.2	55.8	52.5	62	39.7
Median Follow-up (yrs)	5.5	4.5*	2.2*	5.7	3.4	3.9	1.8*
Total Follow-up (pt-yr)	1360	659	411.8	1090	343.5	1069.4	172.5
Target INR	2.0-3.0	2.5-3.5	SoC	2.0-3.0	2.0-3.0	2.5-3.5	1.5-2.5
Mean INR	NR	NR	NR	2.5	NR	NR	43% out of range
NR = Not Reported in the manuscript; * Mean follow-up (yrs) was reported;							
Number of events							
- TE †	8	6	7	19	1	16	2
- Thrombosis	0	0	0	2	0	0	0
- VRM	7	5	1	7	4	19	7
- % TEs in VRM	NR	NR	NR	NR	NR	26% §	NR
Total number of events with 26% reduction to VRM for TE overlap (r)§	13.2	9.7	7.7	30.1 #		30.1	7.2
Linearized event rate with 26% Reduction to VRM for TE overlap (<math>\lambda</math>)§	0.97%	1.47%	1.88%	2.10% #		2.81%	4.16%
Standard error of linearized event rate‡	0.0027	0.0047	0.0068	0.0038		0.0051	0.0155

† Peripheral TE was included if provided; § A 26% VRM was assumed to be related to TE event; # calculated by summing up numbers of events and follow-up years from both high and low risk controls; ‡ calculated as  $\lambda/\sqrt{r}$

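### The pooled warfarin rate of 1.75%/pt-yr (1.09 to 2.81) does not follow from Table 3 by the stated method; on the log scale the six data sets give 2.00 (1.20 to 3.34)

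*Combined protocol and SAP*

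**What the plan says.** Section 8.2 of the protocol presents Table 3 as the summary of the literature, event rates and variances. It pools them by a random-effects HKSJ model in R metafor: "The pooled event rate of warfarin was estimated as 1.75%/pt-yr with a 95% confidence interval of 1.09%/pt-yr and 2.81%/pt-yr". Neither the scale nor the tau-squared estimator is given.

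Table 3 lists six data sets, with the PROACT high- and low-risk controls summed into one. For each it prints the "Total number of events with 26% reduction to VRM for TE overlap (r"), the linearized rate and its standard error.

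The text mentions two further steps. The 65%/35% risk mix in PROACT is something "which was taken into account to estimate the primary outcome rate for the trial". On double counting of deaths it says: "Except for the PROACT clinical trial data, the publications report the non-hierarchical event rate for VRM and TE".

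Section 8.2 then uses the pooled rate and its upper limit several times:
- as the assumed rate in both arms behind N = 990;
- as the basis of the margin, which is "equivalent to a doubling of the estimated event rate in warfarin arm";
- to scale low-risk DAPT results to all comers, where "the conversion factor was calculated to be 1.52 (= 1.75/1.15");
- in the effect 6.85 - 2.81 = 4.04, from which "The non-inferiority margin of 1.75%/pt-yr is approximately 43% (1.75/4.04) of the treatment effect".

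**The concern.** Table 3 prints everything needed to repeat the meta-analysis, and the repeat gives a different answer. Four of the six rates exceed 1.75, and the crude rate over all six data sets is 1.92, so a pooled 1.75 is already surprising.

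At stake is whether the margin justification of a non-inferiority trial can be traced to the table offered in its support. The assumed rate, the conversion factor, the description of the margin, the effect and the margin fraction all inherit the figure.

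**Working it through.** **Inputs (Table 3).** Events are r = TE + thrombosis + 0.74 x VRM, and λ = r / patient-years.

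| Data set | r | pt-yr | λ (%/pt-yr) | ln λ |
|---|---|---|---|---|
| UK, Spain, Greece 2013 | 8 + 0 + 0.74 x 7 = 13.18 | 1360 | 0.97 | -0.031 |
| USA 2006 | 6 + 0 + 0.74 x 5 = 9.70 | 659 | 1.47 | 0.387 |
| Original PMA 2001 | 7 + 0 + 0.74 x 1 = 7.74 | 411.8 | 1.88 | 0.631 |
| PROACT controls, summed | 20 + 2 + 0.74 x 11 = 30.14 | 1433.5 | 2.10 | 0.743 |
| Germany 2007 | 16 + 0 + 0.74 x 19 = 30.06 | 1069.4 | 2.81 | 1.034 |
| South Africa 2006 | 2 + 0 + 0.74 x 7 = 7.18 | 172.5 | 4.16 | 1.426 |

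All printed counts, rates and standard errors (λ/√r) reproduce. The crude rate is 98.00 / 5106.2 = 1.92.

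**Scale.** ln(2.81/1.75) = 0.474 and ln(1.75/1.09) = 0.473, and √(1.09 x 2.81) = 1.75. The stated interval is log-symmetric, so the log scale is the natural reading.

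**Log-scale HKSJ, six rows.** With y = ln λ, v = 1/r and w = 1/(v + τ²):
- μ = Σwy/Σw;
- SE² = Σw(y - μ)² / [(k - 1)Σw];
- interval μ ± t(5 df) x SE, with t = 2.571.

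DerSimonian-Laird (DL) gives τ² = 0.134, μ = 0.694 and SE = 0.198. So 0.694 ± 0.510 becomes 2.00 (1.20 to 3.33). REML and Sidik-Jonkman (SJ) both give 2.00 (1.20 to 3.34).

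**Can τ² explain the gap?** No. The pooled rate is 2.08 at τ² = 0, reaches its minimum of about 2.001 near τ² = 0.2, and is 2.01 at τ² = 1000. The last is in effect the unweighted geometric mean.

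**Other readings, all with the 26% reduction:**

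| Reading | Rate (95% CI) |
|---|---|
| Stated in 8.2 | 1.75 (1.09 to 2.81) |
| PROACT split into its two columns (k = 7), log scale | 1.95 to 1.96 (about 1.23 to 3.10) |
| Raw rates; DL, REML or SJ | 1.88 to 1.93 (lower 0.98 to 1.00, upper 2.79 to 2.86) |
| PROACT weighted 65/35 by risk | 1.97 (1.18 to 3.29) |
| PROACT mortality left unreduced | 2.04 (1.22 to 3.41) |
| South African series dropped | 1.80 (1.08 to 3.00) |

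None of these gives the stated triple. A 49% mortality reduction in place of 26% comes very close: 1.75 (1.09 to 2.81) with SJ and 1.76 (1.10 to 2.80) with DL.

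**What depends on it.** The plan's own chain is 1.75/1.15 = 1.52; all-comer DAPT 10.65 (6.85 to 16.28); 6.85 - 2.81 = 4.04; 1.75/4.04 = 43%. An exponential hazard-difference model at 1.75 gives N of about 989, against 990 stated. With 2.00 (1.20 to 3.34) and the plan's DAPT limits for low-risk patients:
- conversion factor 2.00/1.15 = 1.74;
- DAPT 7.02 x 2.00/1.15 = 12.2, limits 4.51 x 2.00/1.15 = 7.84 and 10.72 x 2.00/1.15 = 18.6;
- effect 7.84 - 3.34 = 4.50;
- margin fraction 1.75/4.50 = 38.9%;
- rate ratio at the margin (2.00 + 1.75)/2.00 = 1.88;
- power with 1000 participants 86.1% (SAP Table 1, row 2.00), against 90.3% at 1.75.

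**The case against.** The strongest reply is that little turns on the difference. The value 2.00 lies inside the stated interval. SAP Table 1 already prints the power at 2.00. The SAP's sample size section (6.1.8 in version 1.4) admits uncertainty about the background rate and points to the OPC test and a hazard-ratio sensitivity analysis. The margin fraction improves. SAP version 1.4, section 6.1.3, records that the study was stopped on DSMB advice, so restated power has no prospective effect. All of this stands, and it limits the size of the point. It does not make 1.75 follow from Table 3.

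A second reply is that scale and estimator are unstated, so some other choice may lie behind 1.75. That is fair as a reason to ask for the inputs first. But no scale, estimator or subset tried with the 26% reduction gives the stated rate and interval. Splitting PROACT lowers the rate only to about 1.95, and the Table 3 footnote says the two columns were summed.

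A reader might also infer an error in the DAPT limits, "20.2 (13.00, 30.89) using the Poisson distribution", because 13.00 is the exact lower limit for 21 events and 30.89 the exact upper limit for 20. The documents do not support that. Direct Poisson inversion at a fractional count gives exactly these values, since P(X ≥ 20.2) = P(X ≥ 21) and P(X ≤ 20.2) = P(X ≤ 20). The same convention reproduces all ten apixaban intervals in Table 2 to within 0.01, at a fitted follow-up of about 1186 pt-yr (not stated in the plan). The convention yields a narrow interval, but that is a separate methods point and no correction is required here.

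**Conclusion.** Wrong as written. The pooled rate and interval do not follow from Table 3 by the stated method. On the log scale the result is 2.00 (1.20 to 3.34), about 0.25%/pt-yr higher. This rests on Table 3 as printed, PROACT entered as one data set, and the log scale inferred from the interval.

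Three stronger readings are not supported:
- **That the margin fails the one-half criterion.** The fraction falls from 43% to about 39%. The Table 2 argument for a 5% apixaban rate also survives, since its upper limit of 6.42 is below 7.84.
- **That the trial was underpowered.** The 86% is the plan's own figure at 2.00, and the rate pooled here includes valve-related mortality, which the tested outcome in section 8.1 does not.
- **That the cause is known.** The near match at a 49% reduction suggests that the inputs used may differ from those printed. It is an inference only, and the documents cannot show which of the two is at fault.

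The defect is one of traceability and of planning figures. It does not reach the test or the decision rule.

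**What to change.** First, state in section 8.2 the rows, event counts, scale and tau-squared estimator that produced 1.75. Then take one of two routes.

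1. If other inputs were used, correct Table 3 and the text of 8.2 to match them.
2. Otherwise restate the rate as 2.00 (1.20 to 3.34) in 8.2 and Table 2 and carry it through, keeping the plan's Poisson convention for DAPT: conversion factor 1.74; DAPT 12.2 (7.84 to 18.6); effect 4.50; margin fraction about 39%; margin described as a rate ratio of about 1.88 rather than a doubling; power about 86% with 1000 participants at 2.00.

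On either route, say that these figures apply to the composite that includes valve-related mortality.

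The cost is one rerun of the meta-analysis and some restated figures. Margin, tests and sample size do not change. The downside of the second route is a slightly less favourable stated power.

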**Table 2. Event rates and confidence intervals for warfarin, DAPT, and apixaban in all-comer AVR population.**

Treatment in all-comer AVR population	Event rate (%/pt-yr)	Lower 95% CI (%/pt-yr)	Upper 95% CI (%/pt-yr)
Warfarin*	1.75%	1.09%	2.81%
DAPT†	10.65%	6.85%	16.28%
Apixaban†	1.00%	0.52%	1.66%
	1.25%	0.71%	1.98%
	1.50%	0.90%	2.30%
	1.75%	1.10%	2.60%
	2.00%	1.30%	2.91%
	2.25%	1.50%	3.21%
	2.50%	1.71%	3.51%
	3.00%	2.13%	4.10%
	4.00%	2.98%	5.27%
	5.00%	3.86%	6.42%

\* The confidence interval was estimated using the random effects HKSJ meta-analysis model; † The confidence intervals were estimated using Poisson distribution.

Assuming that the event rates for warfarin and apixaban would be similar, a conservative estimate of the treatment effect is 4.04%/pt-yr, which reflects the difference between the upper bound of the 95% CI of the pooled event rate of warfarin (2.81%/pt-yr) and the lower bound of the 95% CI of the event rate in DAPT (6.85%/pt-yr). The non-inferiority margin of 1.75%/pt-yr is approximately 43% (1.75/4.04) of the treatment effect and below ½ of the treatment effect as cited in the 2016 FDA guidance “Non-Inferiority Clinical Trials to Establish Effectiveness Guidance for Industry” ([CDER/FDA, 2016](#)).

With an accrual time of 1 year, an assumption that 50% of the expected number of participants will be enrolled in about 5 months (40% of the total accrual time), and a minimum follow-up period of 2 years, the assumed loss to follow-up rate for the period of 2 years is 5%, which is equivalent to a loss hazard rate of 0.026 for both the test and control groups. *Assuming a one-sided alpha of 2.5%, an approximate power of 90%, an equal event rate of 1.75%/pt-yr in both warfarin and apixaban arms, and an absolute NI margin of 1.75%/pt-yr, the estimated sample size is 990, therefore this study will recruit approximately 1000 participants.*

The major bleeding hazard rate for the control group is assumed to equal 3.63%/pt-yr ([Puskas et al., 2018](#)). The reference value was calculated by summing up numbers of events and follow-up years from both high and low risk controls. Using the proposed sample size of 1000, a superiority test for major bleeding has 90% power to detect a difference of 2.13%/pt-yr (i.e., 3.63%/pt-yr for warfarin arm and 1.5%/pt-yr for apixaban arm).

All sample size calculations were done via PASS 16.0.5 (released May, 2019) using Non-Inferiority and Inequality Tests for the Difference of Two Hazard Rates Assuming an Exponential Model for the primary efficacy outcome and Tests for the Difference of Two Hazard Rates Assuming an Exponential Model for the primary safety outcome.

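### Protocol 8.2 pairs Poisson limits from two different counts for DAPT; with exact limits from one count the margin is 47-48% of the warfarin effect, not 43%, and still below one half

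*Combined protocol and SAP*

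**What the plan says.** All of this is in protocol section 8.2, with inputs from section 11, Table 4. Both SAP versions refer back to section 8.2 for the margin justification.

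- The DAPT arm of the earlier On-X trial had 14 thromboembolic events, 4 thromboses and 3 valve-related deaths in 288.1 pt-yr. With deaths reduced by 26% for overlap, the count is 20.2.
- The stated interval is: "DAPT in the low risk population is 20.2 (13.00, 30.89) using the Poisson distribution". As rates this is 7.02%/pt-yr (4.51 to 10.72).
- A factor of 1.52 carries these to an all-comer population: 10.65%/pt-yr (6.85 to 16.28).
- The conservative treatment effect is the DAPT lower limit minus the pooled warfarin upper limit of 2.81%/pt-yr, printed as 4.04%/pt-yr.
- The conclusion is: "The non-inferiority margin of 1.75%/pt-yr is approximately 43% (1.75/4.04) of the treatment effect", which the protocol then notes is less than half.
- For a 5%/pt-yr apixaban rate, the protocol says that "the estimated upper 95% CI of the apixaban arm will still remain below the lower 95% CI of the event rate of DAPT". Table 2 prints 6.42 and 6.85 for these two limits.
- The Table 2 footnote gives the method for the DAPT and apixaban rows only as "The confidence intervals were estimated using Poisson distribution". It gives no formula, and no exposure for the apixaban rows.

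**The concern.** An interval for one count should take both limits from that count. The printed pair does not, and the lower limit is the one that is too high. That limit is the starting point for 6.85, then 4.04, then 43%, so the error enlarges the warfarin effect in a calculation that is presented as conservative.

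The protocol acknowledges that no placebo-controlled warfarin trial exists in this population. The chain from about 20 DAPT events is therefore its only quantitative support for the claim that the margin preserves at least half of warfarin's effect. A reader who weighs the other assumptions in that chain (DAPT standing in for placebo, and the 1.52 extrapolation) needs to know how much room is really left below one half.

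**Working it through.** **Inputs.** Count 20.2 and exposure 288.1 pt-yr (section 11, Table 4); factor 1.52, warfarin upper limit 2.81%/pt-yr and margin 1.75%/pt-yr (section 8.2). The 2.81 is taken as stated.

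**Step 1: reproduce the plan's figure.** 13.00/288.1 = 4.51%/pt-yr. 4.51 × 1.52 = 6.86, printed as 6.85 (rounding of the factor). 6.85 − 2.81 = 4.04. 1.75/4.04 = 43.3%. The 43% follows from the printed lower limit.

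**Step 2: check the limits.** The exact 95% Poisson limits for a count r are

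- lower = χ²(0.025; 2r)/2
- upper = χ²(0.975; 2(r+1))/2

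For a fractional count the same formulas give the gamma form.

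| Count | Lower | Upper |
|---|---|---|
| 20 | 12.22 | **30.89** |
| 20.2 | 12.37 | 31.13 |
| 21 | **13.00** | 32.10 |
| Printed for 20.2 | 13.00 | 30.89 |

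The printed lower limit belongs to 21 events and the printed upper limit to 20. Eight other constructions were tried at 20, 20.2, 20.22 (unrounded) and 21 events: mid-P (whole counts only), Wald, log-Wald, score, Byar, square-root, Jeffreys and Poisson quantiles. None gives both printed limits from one count.

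**Step 3: carry one-count exact limits through the chain.**

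| Quantity | Printed | 20 events | 20.2 events |
|---|---|---|---|
| DAPT lower limit, low risk (%/pt-yr) | 4.51 | 12.22/288.1 = 4.24 | 12.37/288.1 = 4.29 |
| × 1.52, all-comer | 6.85 | 6.45 | 6.53 |
| − 2.81 = treatment effect | 4.04 | 3.64 | 3.72 |
| Half the effect | 2.02 | 1.82 | 1.86 |
| 1.75 / effect | 43.3% | 48.1% | 47.1% |

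The room below 50% falls from 6.7 points to between 1.9 and 2.9 points.

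**Step 4: is it a slip in one number?** The apixaban rows of Table 2 suggest not. Their exposure is not stated, so it was searched from 900 to 1,500 pt-yr. Rounding the expected count up for the lower limit and down for the upper limit reproduces all 20 printed limits to within 0.005 at 1,186 pt-yr. Exact limits on the unrounded count match at most 8 of the 20 at any exposure searched. Three rows at 1,186 pt-yr:

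| Rate | Expected events | Counts used (lower, upper) | Mixed rule | Printed | One count |
|---|---|---|---|---|---|
| 1.00% | 11.86 | 12, 11 | 0.52-1.66 | 0.52-1.66 | 0.51-1.75 |
| 1.75% | 20.76 | 21, 20 | 1.10-2.60 | 1.10-2.60 | 1.08-2.68 |
| 5.00% | 59.3 | 60, 59 | 3.86-6.42 | 3.86-6.42 | 3.81-6.45 |

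The 1.75% row uses the same pair as the DAPT interval: 13.00/1,186 = 1.10% and 30.89/1,186 = 2.60%.

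**Step 5: the 5% apixaban statement.** The printed gap is 6.85 − 6.42 = 0.43. With the gamma form for both arms it is 6.53 − 6.45 = 0.08. With whole numbers for both (59 apixaban events, 20 DAPT events) it is 6.45 − 6.42 = 0.03. The statement stays true, with a much smaller gap.

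**The case against.** **The conclusion survives.** The protocol's claim is that the margin is less than half the effect, and at 47-48% it still is. Sample size, power and the decision rule do not use the DAPT limits. This stands in full: the point corrects a reported figure and does not challenge the design.

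**Exact limits are a choice.** The protocol says only that a Poisson distribution was used, and 20.2 is not a whole number, so no strictly exact interval exists for it. Other one-count methods on 20 to 20.2 events give shares of about 43-44% (score, log-Wald), 45-46% (Jeffreys, mid-P) and 55-56% (Wald). This stands as a limit on the claim: 47-48% is the result for exact limits and not the only defensible figure. It does not rescue the printed interval. The closest rival is the score form, r + 1.92 ± 1.96√(r + 0.96), which for 20 events gives 12.95 to 30.89. It misses the printed lower limit, and score limits match at most 3 of the 20 apixaban limits. Using 21 events throughout would keep 43%, but it contradicts the stated 20.2 and would need an upper limit of 32.10.

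**The interval is not plainly too narrow at both ends.** For a count of 20 the printed upper limit is right and only the lower limit is wrong. Both ends are too narrow only against 20.2. The upper limit plays no part in 4.04 or 43%.

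**The apixaban exposure is fitted.** That is so. The fit is close, but 1,186 pt-yr appears nowhere in the documents, and those rows do not feed the margin.

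**Larger uncertainties exist.** The 1.52 factor rests on 4.0 low-risk warfarin events and is treated as known, and DAPT is taken as equivalent to placebo. Those assumptions may well matter more, which is a reason to state the share correctly and not a reason to leave it.

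**Conclusion.** The DAPT interval in section 8.2 combines limits from two counts, and the 6.85, 4.04 and 43% that depend on its lower end need restating. With exact limits on 20 to 20.2 events they become 6.45-6.53%/pt-yr, 3.64-3.72%/pt-yr and 47-48%. This rests on exact (or gamma-form) limits, on the stated count and exposure, and on the 1.52 factor and the 2.81 warfarin limit as given.

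A reader might infer three stronger things, and the documents support none of them:

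- *That the margin fails the one-half criterion.* It does not: half the corrected effect is 1.82-1.86%/pt-yr, above 1.75.
- *That the trial is wrongly sized.* The 990 comes from the event rates, the margin, alpha, power and follow-up, none of which changes.
- *That the 5% apixaban statement is now false or a tie.* An apparent tie of 6.45 against 6.45 arises only by setting a gamma-form apixaban limit beside a whole-number DAPT limit, which again mixes counts. Under either consistent rule the statement holds, by about 0.03-0.08%/pt-yr at the inferred exposure.

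**What to change.** 1. Recompute every Poisson limit in section 8.2 and Table 2 from one count per row. Name the method, say how fractional counts are handled, and state the exposure assumed for the apixaban rows.
2. Restate the DAPT limits, the treatment effect (about 3.6-3.7%/pt-yr) and the margin share (47-48%) if exact limits are kept. If another method is chosen, give its own figures and the reason for choosing it.
3. Keep the 5% apixaban statement, and report the gap as about 0.03-0.08%/pt-yr (6.42 against 6.45, or 6.45 against 6.53) in place of the 0.43 implied by the printed table.

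The cost is a few corrected numbers and a method note in the protocol. The stated share becomes less favourable. The margin, sample size, power and analysis do not change, and the SAP needs no edit on this point because it refers to section 8.2.

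### Protocol 8.2 does not establish that the margin is below half of warfarin's effect: the 1.52 conversion factor rests on about four events and is used as if exact

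*Combined protocol and SAP*

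**What the plan says.** Protocol Section 8.2 sets the margin at 1.75%/pt-yr, described as "equivalent to a doubling of the estimated event rate in warfarin arm". It then tries to show that this margin keeps part of warfarin's effect. With no placebo-controlled data available, it uses the low-risk stratum of the PROACT trial and lets DAPT stand in for placebo. Table 4 gives 1.15%/pt-yr on warfarin and 7.02%/pt-yr on DAPT.

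To move from low-risk to all-comer patients, "the conversion factor was calculated to be 1.52 (= 1.75/1.15"). The event count "of DAPT in the low risk population is 20.2 (13.00, 30.89) using the Poisson distribution" becomes 4.51 to 10.72%/pt-yr. Multiplied by 1.52, this gives the Table 2 entry of 10.65 (6.85 to 16.28).

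The effect is put at 4.04%/pt-yr, "which reflects the difference between the upper bound of the 95% CI of the pooled event rate of warfarin (2.81%/pt-yr") and the DAPT lower limit of 6.85. From this follows "The non-inferiority margin of 1.75%/pt-yr is approximately 43% (1.75/4.04) of the treatment effect", which the protocol places below one half with reference to the 2016 FDA guidance. It adds that even at an apixaban rate of 5%/pt-yr "the estimated upper 95% CI of the apixaban arm will still remain below the lower 95% CI of the event rate of DAPT". Both SAP versions refer back to Section 8.2 for the margin justification.

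**The concern.** The factor 1.52 is treated as a known constant, although its denominator comes from one thromboembolism and four valve-related deaths, the deaths reduced by 26%. No interval is given for 1.15 or 1.52. The DAPT interval therefore carries only the Poisson error of the DAPT count and is too narrow.

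The rule also uses two warfarin rates: the factor is built on 1.75, and then 2.81 is subtracted. This understates the effect and partly offsets the missing error, by an amount the plan does not state.

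Two smaller points sit alongside:

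- The printed Poisson interval for 20.2 events joins limits that belong to two different counts.
- Section 8.2 says "Except for the PROACT clinical trial data, the publications report the non-hierarchical event rate for VRM and TE", which exempts PROACT from double counting. Tables 3 and 4 nevertheless apply the 26% reduction to PROACT deaths (Table 3 footnote: "A 26% VRM was assumed to be related to TE event").

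This calculation is the only support for saying that the margin preserves a share of warfarin's effect. If it does not hold, meeting the margin cannot be reported as keeping at least half of that effect.

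**Working it through.** **Inputs.** Margin 1.75; pooled warfarin rate 1.75 (1.09 to 2.81), taken as the plan gives it (Section 8.2). Low-risk warfarin: 1 + 0 + 0.74 × 4 = 3.96 events in 343.5 pt-yr. Low-risk DAPT: 14 + 4 + 0.74 × 3 = 20.22 events in 288.1 pt-yr (Table 4). Rates are in %/pt-yr.

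**1. The plan's figure.** 3.96/343.5 = 1.15; 20.22/288.1 = 7.02; 1.75/1.15 = 1.52; 4.51 × 1.52 ≈ 6.85; 6.85 − 2.81 = 4.04; 1.75/4.04 = 43%. It reproduces.

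**2. Sensitivity to the small count, factor error still ignored.** With w low-risk warfarin events, the plan's share is 1.75 / [4.51 × 1.75/(w/3.435) − 2.81]. This is 43% at w = 3.96, 50% at 4.30 and 67% at 5. With one warfarin rate throughout, the share is 34% (at 1.75) or 21% (at 2.81), and one half is reached at w = 5.17 or 6.90. All these counts lie inside the exact 95% interval for 3.96 events, 1.07 to 10.18.

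**3. Factor error carried.** Scaling DAPT by b/1.15 is the same as b × R, where b is the all-comer warfarin rate and R = 7.02/1.15 = 6.09 (from unrounded rates) is the low-risk DAPT/warfarin ratio. The effect is b(R − 1). With the lower 95% limit R_L, the share is 1.75/[b(R_L − 1)]. A share of one half needs R_L = 1 + 3.5/b, which is 4.21 at b = 1.09, 3.00 at 1.75 and 2.25 at 2.81.

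Log-Wald: SE(log R) = √(1/20.22 + 1/3.96) = 0.550; 6.09 × exp(±1.96 × 0.550) gives 2.07 to 17.9.

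| Method for R_L | R_L | Share at 1.75 | Share at 2.81 |
|---|---|---|---|
| Conditional exact, 20 v 4 | 2.00 | 100% | 62% |
| Conditional exact, 20.22 v 3.96 | 2.03 | 97% | 60% |
| Log-Wald | 2.07 | 93% | 58% |
| Score | 2.17 | 85% | 53% |
| Gamma, 0.5 added to each count | 2.27 | 79% | 49% |
| Profile likelihood | 2.30 | 77% | 48% |
| Gamma, no addition | 2.40 | 71% | 44% |

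No method reaches 3.00. The limits fall on both sides of 2.25.

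**4. Confidence that the share is below one half (log-Wald, one-sided).** At 1.75: z = ln(6.09/3.00)/0.550 = 1.29, about 90%. At 2.81: z = ln(6.09/2.25)/0.550 = 1.81, about 96.5%. A 95% limit stands for 97.5%.

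**5. Checks that do not depend on this rule.**

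- Direct low-risk difference, no conversion factor: 7.02 − 1.15 = 5.87. The lower limit is 5.87 − 1.96 × 100 × √(20.22/288.1² + 3.96/343.5²) = 2.60, so the share is 1.75/2.60 = 67%.
- Ratio and pooled-rate errors carried jointly, assuming a lognormal pooled rate matching 1.09 to 2.81: the lower limit of the effect is 2.0 to 2.3, a share of about 77% to 86%.
- Plan's own subtraction kept, factor error carried: 1.75 × R_L − 2.81 = 0.68 to 1.40, so the margin is 125% to 256% of the effect.

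**6. The 5%/pt-yr sentence.** Table 2 gives an apixaban upper limit of 6.42 at that rate. The DAPT lower limit b × R_L becomes 3.5 to 4.2 at b = 1.75, so the sentence fails. At b = 2.81 it is 5.6 to 6.8. The sentence then needs R_L above 6.42/2.81 = 2.28, which only the profile (2.30) and unadjusted gamma (2.40) limits exceed.

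**7. Smaller points.**

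- Exact Poisson limits are 12.22 to 30.89 for 20 events and 13.00 to 32.10 for 21. The printed pair takes its lower limit from 21 and its upper limit from 20. The gamma-extended limits for 20.22 are 12.39 to 31.16. With 12.39 alone corrected, 43% becomes 47%.
- Without the 26% cut the PROACT counts are 5 and 21. Holding 1.75 fixed, the factor is 1.75/(5/3.435) = 1.20, the DAPT lower limit is 5.42 and the plan's share is 1.75/(5.42 − 2.81) = 67%.
- The apixaban rows of Table 2 fit the same mixed pairing at an exposure of about 1,186 pt-yr. The documents do not state the exposure, so this is an inference.

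**The case against.** The 43% is correct arithmetic on the plan's chosen inputs, and the plan leans cautious in two places. It takes the unfavourable limit on each side, and it treats DAPT as a placebo equivalent, which should understate warfarin's effect. With the factor fixed, single-rate versions give lower shares (34% and 21%). At the point estimates the share is 1/(6.09 − 1), about 20%. At 2.81 three methods give less than one half and the log-Wald confidence falls only a point short of 97.5%. The 100% end of the range uses rounded counts; at 20.22 and 3.96 the range is 71% to 97%.

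The 26% cut to PROACT deaths also follows a rule in Section 8.2, which applies it wherever deaths from thromboembolism were not reported; Table 3 lists PROACT as not reported. Little is decided by this passage: the planned success statement claims only a reasonable alternative to warfarin, and success also requires the objective performance criterion (OPC) test, which does not use the factor.

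All of this stands as qualification. It does not supply the missing error. Subtracting 2.81 does not make up for it: carrying both errors jointly still leaves the share above one half, as does the direct low-risk difference. The PROACT cut remains a conflict between two statements in one section, and the documents do not show which is right.

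**Conclusion.** The concern holds. The below-one-half statement is not established once the error in the conversion factor is carried. At 1.75%/pt-yr, the rate the margin doubles, the margin is 71% to 100% of the lower-bound effect on every method tried. At 2.81%/pt-yr the answer depends on the method (44% to 62%). This does not show that the margin exceeds half of the true effect; it shows that the PROACT data are too sparse to rule that out at the usual confidence.

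The result rests on Poisson counts, on the adjusted counts in Table 4, on carrying the low-risk ratio over to all-comers as the plan does, and on DAPT as the reference. The consequence is limited to how the margin is justified and described. SAP version 1.4, Section 6.1.3, records that the DSMB stopped the study, so no design decision remains open on this point.

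**What to change.** In Protocol Section 8.2 and Table 2:

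1. Recompute the DAPT limits with one named Poisson method. Recompute the apixaban rows the same way from the sponsor's own assumed exposure, and state that exposure.
2. Derive the all-comer DAPT interval from the DAPT/warfarin rate ratio with its confidence interval, naming the method and using one warfarin rate throughout. Report effect and share at 1.75, with 1.09 and 2.81 as sensitivity values. In ratio form a higher warfarin rate gives a larger effect, so 2.81 is not the cautious choice.
3. Delete the statement that the margin is below one half of the effect unless it survives step 2. Otherwise write: *The margin equals a doubling of the assumed warfarin rate; it has not been shown to preserve half of warfarin's effect as estimated against DAPT.*
4. Revise the 5%/pt-yr sentence to match the new DAPT interval.
5. Reconcile the sentence exempting PROACT from double counting with the 26% reduction in Tables 3 and 4.

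The cost is recalculation and rewording. Margin, sample size, test and OPC criterion stay as they are. The downside is a less favourable statement about the margin.
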